### 2.3.3 **Exploratory outcomes**

Although power will be lower for some of these analyses, they are included because of their importance in improving cancer outcomes.

- (i) Patient care experience measured by the Australian Hospital Patient Experience Question Set (AHPEQS) [19]
- (ii) Survival; information about date and cause of death or date last known to be alive will be obtained from medical records. This will be assessed passively from medical records and via data-linkage after the main trial is complete.
- (iii) Partner/carer distress and unmet supportive-care needs measured by the HADS and Supportive Care Needs Survey – Partners and Carers (SCNS-P&C) [22].

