### **2.5.2 Potential Benefits**

Potential benefits to participants in the intervention group (and their partners/carers) include enhanced communication with their clinical team, earlier identification of potential problems, more timely intervention and thus a better outcome.

There is unlikely to be any direct benefit to participants in the control group although, as described in 2.5.1, if control participants report severe distress on a study questionnaire we will report this to their clinical team and this may result in more effective management of the problem.

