#### **4.3.2 *Blinding Procedures***

All study staff/investigators will be blinded to the allocation sequence ensuring allocation concealment until study entry. Due to the nature of the intervention, participants, their treating clinicians and the Trial Coordinators at each site will not be blinded to group allocation; however, the other investigators and project staff, including those collecting outcome data and conducting analyses, will remain blinded until after the main analyses have been finalised and the first papers are being prepared for publication (see 10.3 Statistical Analysis).

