## 10. **STATISTICAL CONSIDERATIONS**

### 10.1 **Study Hypotheses**

We hypothesise that, compared to usual care, routine self-reporting of e-PROMs will result in:

1. Primary Outcomes:
  - Fewer emergency presentations/unplanned hospital admissions;
  - Better physical and functional well-being at 6 months;
2. Secondary Outcomes:
  - Higher rates of treatment completion;
  - Better health-related quality of life (HRQOL);
  - Lower rates of distress;
  - Lower symptom burden;
  - Fewer out-patient visits;
3. Exploratory Outcomes:
  - A better patient care experience;
  - Better survival;
  - Lower rates of distress and unmet supportive care needs among partners/carers.

We also hypothesise that use of the e-PROM tools will be cost-effective compared to usual care.

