### 10.3.3 *Exploratory Outcomes*

**Survival:** we will calculate and the mortality rate (per person-year) in each group and use Cox proportional hazards regression to compare mortality in the two study groups.

**A better patient care experience:** the AHPEQS asks patients to rate 9 aspects of care on a 5-point scale from never (worst) to always (best) and their overall care from very poor to very good. We will use chi-squared tests to compare the proportions of participants in each group that answer mostly or always to each individual item (or good/very good to overall care) and t-tests to compare the mean number of items rated as mostly/always. We will also

compare the proportions of participants who report experiencing physical and/or emotional distress and, among those who report distress, the proportions who reported that healthcare staff discussed this with them.

**Partner/Carer distress and unmet supportive-care needs:** HADs data from carers will be analysed as for participants (above). Analyses of supportive-care needs will compare the frequency of individual needs and specific domains (information needs, healthcare needs, psychological and emotional needs, social and work needs). Parametric and non-parametric tests, as appropriate, will be used to compare the intervention and control groups.

**Sub-group analyses:** We will repeat the primary and secondary analyses above for sub-groups of participants defined by (i) study site, (ii) e-PROM tool (*My Health My Way* vs. *AboutMe*), (iii) cancer type (high vs. low mortality), (iv) type of treatment (curative/palliative), (v) sex, and (vi) computer literacy. This is to examine effect modification and identify scenarios where e-PROM tools are potentially most effective and those where their effectiveness could be improved. We recognise that statistical power will be more limited for some of these stratified comparisons.

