### **14.5 Appendix E: Curriculum Vitae**

## **APPENDIX A: SCHEDULE OF EVENTS**

	T0	T3	T6	T12	T18	T24	>T24
Informed study consent	✓						
MBS/PBS data consent	✓						
Carer & Genetic Substudy consent	✓						
Medical history/co-morbidities	✓						
Cancer diagnosis/treatment	✓						
Intervention (Intervention Group only)							
Blood sample	✓		✓				
Collect clinical data	✓			✓		✓	✓
QUESTIONNAIRES							
Demographics (Participants & Carers)	✓						
FACT-G (Participants)	✓	✓	✓	✓	✓	✓	
HADS (Participants & Carers)	✓	✓	✓	✓	✓	✓	
MSAS (Participants)	✓	✓	✓	✓	✓	✓	
EQ-5D (Participants & Carers)	✓	✓	✓	✓	✓	✓	
Patient Experience (AHPEQS) (Participants)			✓	✓	✓	✓	
System Usability Survey (Participants)			✓				
Supportive Care Needs Survey (Carers)	✓	✓	✓	✓	✓	✓	
QUALITATIVE INTERVIEWS							
Participants & Carers					✓		
Clinicians					✓		✓
DATA LINKAGE							
Health resource utilisation				✓		✓	✓

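### The between-arm comparison of whether staff discussed distress is restricted to participants who report distress after randomisation, so it can be biased in either direction

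*Protocol*

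**What the plan says.** Protocol section 2.3.3 lists as exploratory "Patient care experience measured by the Australian Hospital Patient Experience Question Set (AHPEQS"). In section 10.3.3 the analysis has two linked parts. The first, over all participants, is to "compare the proportions of participants who report experiencing physical and/or emotional distress". The second is to compare, "among those who report distress, the proportions who reported that healthcare staff discussed this with them". No version of the second comparison uses all respondents, and no caveat is attached to it.

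Other sections that bear on it:

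- Appendix A, row "Patient Experience (AHPEQS) (Participants"), is ticked at T6, T12, T18 and T24 and blank at T0 and T3.
- Section 10.1 hypothesises "Lower rates of distress" and "Lower symptom burden" with the intervention. Sections 2.3.2 and 10.3.2 measure these by HADS and MSAS respectively.
- Section 2.5.2 expects for the intervention group "enhanced communication with their clinical team, earlier identification of potential problems, more timely intervention and thus a better outcome".
- Section 4.3.2 states that "participants, their treating clinicians and the Trial Coordinators at each site will not be blinded to group allocation".

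**The concern.** Who enters the denominator is decided by an answer given at 6 months or later. If the intervention changes which participants report distress, the two distressed groups are no longer alike apart from allocation. A difference in the discussion percentage could then reflect a different mix of severity and not different behaviour by staff.

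A change of mix is plausible here. The AHPEQS item covers physical and emotional distress, which lie close to the two domains that the trial hopes to improve. Discussion is also likely to depend on severity: under sections 5.1 and 5.1.1 the tool grades symptoms, builds a risk profile and, in one of the two systems, sends alerts above set thresholds. Because participants know their allocation, the readiness to report distress may differ by arm as well.

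At stake is the reading of one item. It asks whether staff took up the patient's distress, which is close to the process that the tool is meant to improve, so a spurious difference in either direction could be taken as evidence on how the tool works.

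**Working it through.** The protocol states no figure for this comparison, so there is none to reproduce. The check asks whether the contrast can move when discussion at each severity is identical in both arms.

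**Inputs**

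- About 200 respondents per group: section 10.2 recruits 286 per group and allows 30% drop-out, and 286 × 0.70 = 200.2.
- Assumed: 50% of controls report distress, half mild and half severe, which is 50 mild and 50 severe.
- Assumed: staff discuss mild distress with probability 0.4 and severe distress with probability 0.8, in both arms.

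**Formulas**, with m and s the numbers reporting mild and severe distress:

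- Conditional percentage = (0.4m + 0.8s) / (m + s)
- Distress not discussed, over all respondents = (0.6m + 0.2s) / 200

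**Results**

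| Case | m, s | Conditional percentage | Not discussed, all respondents |
|---|---|---|---|
| Control | 50, 50 | (20 + 40)/100 = 60.0% | (30 + 10)/200 = 20.0% |
| Severe halved | 50, 25 | (20 + 20)/75 = 53.3% | (30 + 5)/200 = 17.5% |
| Mild halved | 25, 50 | (10 + 40)/75 = 66.7% | (15 + 10)/200 = 12.5% |
| Both fall 25% | 37.5, 37.5 | (15 + 30)/75 = 60.0% | (22.5 + 7.5)/200 = 15.0% |
| Mild reported 50% more often | 75, 50 | (30 + 40)/125 = 56.0% | (45 + 10)/200 = 27.5% |

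Staff behave identically in every row, yet the conditional percentage moves by −6.7, +6.7, 0 or −4.0 points.

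**Sensitivity, severe distress halved**

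- Discussion probabilities 0.6/0.6: no shift.
- 0.5/0.7: (25 + 17.5)/75 = 56.7%, a shift of −3.3 points.
- 0.3/0.9: (15 + 22.5)/75 = 50.0%, a shift of −10.0 points.

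**Chance of a false finding.** For a two-sided 5% test of two proportions with 100 against 75 distressed respondents, the chance of a significant result in the false direction is 14.1% at 0.4/0.8. It is 6.5% at 0.5/0.7 and 26.0% at 0.3/0.9, against 2.5% nominal in one direction. If 30% to 70% of controls report distress, the range over these three pairs is 5.3% to 34.4%.

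**The case against.** The strongest reply is that the question has meaning only for people with distress, and that the protocol already compares reported distress over all participants. From the two planned figures a reader can derive undiscussed distress: in the severe-halved case, 0.375 × (1 − 0.533) = 17.5%, against 0.50 × (1 − 0.60) = 20.0% in controls. This stands as far as it goes. A shift in the denominator would be visible, but seeing it does not make the conditional contrast a randomised one.

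It is also fair that the alternative measure is not neutral. With identical staff behaviour it shows 20.0% against 15.0% when both severities fall by a quarter, whereas the conditional percentage is rightly unchanged. The two answer different questions.

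A reader might infer more than the protocol supports:

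- *That the denominator is itself an outcome the trial predicts will fall.* The distress hypothesis is tied to HADS and the symptom hypothesis to MSAS. That the AHPEQS item moves with them is a reasonable inference, not a statement in the protocol.
- *That the tool will look harmful because patients whose distress was discussed and resolved leave the denominator.* This needs resolved distress to go unreported. The item's wording and recall period are in Appendix D, which is listed only by file name, and a patient may still report distress that has since resolved.
- *That the comparison breaches the intention-to-treat statement in section 10.3.* It is still made by allocated arm, but within a subset defined after randomisation.

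Finally, section 10.3.3 names chi-squared tests for the rating items and for this item says only that proportions are compared. The false-finding chances above apply only if a test is run.

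**Conclusion.** The point holds as a minor one. The comparison conditions on a status measured after randomisation that the intervention may plausibly change, so a difference between arms cannot be read as a difference in how often staff discuss distress. The direction is not fixed. Under the assumed inputs the shift is about 7 points either way, with a range of 3 to 10 points as the dependence of discussion on severity varies. It is nil if severities fall proportionally or discussion does not depend on severity.

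This rests on two things that the protocol does not settle: that the intervention changes the severity mix of those who report distress on the AHPEQS, and that discussion depends on severity. All distress and discussion rates used here are assumptions. The outcome is exploratory, and no sample size, decision rule, primary result or secondary result depends on it.

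**What to change.** In section 10.3.3, add a between-arm comparison over all randomised respondents of a three-level outcome: no distress reported, distress reported and discussed, distress reported and not discussed. Keep the conditional percentage as a descriptive figure, with a note that randomisation does not protect it.

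The cost is about one sentence. The data are already collected, and neither sample size nor conduct changes. There is a small downside: the all-respondent measure combines how often distress occurs with whether it is discussed, so it should be read alongside the planned comparison of reported distress. It also does not remove questionnaire non-response or differences in reporting between unblinded arms; in the last row of the table, extra reporting of mild distress raises undiscussed distress from 20.0% to 27.5%.

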### **4.3 Treatment Assignment Procedures**

#### **4.3.1 *Randomisation Procedures***

Randomisation will be at the patient level, with a 1:1 ratio between groups, using randomly varied permuted blocks, stratified by sex, hospital, treatment intent (curative/palliative) and computer literacy (defined as regular access to a computer/tablet/smart phone and use of email  $\geq 1$ /week vs. less often) as this was shown to be important in previous trials [8, 9]. When a participant completes the Baseline Study Questionnaire, the central web-based database will automatically apply the next relevant record in the allocation sequence, as we have done previously [24-26].

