### 10.3.2 *Secondary Outcomes*

**Higher rates of treatment completion:** we will calculate the fraction of planned primary treatment that participants actually received. We will compare the mean (or median, as appropriate) fraction received and the proportion of participants who received >85% of their planned treatment between the groups using t-tests and chi-squared tests, respectively.

**Better overall HR-QoL, lower rates of distress and lower symptom burden:** we will calculate overall FACT-G (to measure HR-QoL), HADS anxiety and depression (to measure distress) and MSAS (to measure symptom burden) scores at each time point. If there are missing items, subscale scores will be prorated as per the relevant scoring manuals. We will use t-tests to compare the intervention and control groups with respect to absolute levels at each time-point (with 6 months being the primary time-point) and will use mixed effects repeated measures models to assess change over time from baseline. The models for post-randomisation point will be adjusted for baseline score and stratification factors. A difference of 0.5 standard deviations on each scale is considered clinically meaningful.

We will also assess differences in social and emotional wellbeing using these subscales of FACT-G.

**Fewer out-patient visits:** we will use Poisson regression to calculate and compare the rate of unplanned hospital presentations (per 10,000 patient days) during follow-up in each group.

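### Carers' supportive-care needs are compared with plain two-group tests although a T0 survey is scheduled: a minor, avoidable loss of precision on an exploratory outcome

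*Protocol*

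**What the plan says.** Partner/carer distress and unmet supportive-care needs form a single exploratory objective (sections 2.2.3 and 2.3.3), and section 10.3.3 gives the analysis of each half.

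- **Distress (HADS):** "HADs data from carers will be analysed as for participants (above"). For participants, section 10.3.2 prescribes t-tests on absolute levels at each time-point, with 6 months as the primary one, and mixed-effects repeated-measures models for change over time. Of the models it says: "The models for post-randomisation point will be adjusted for baseline score and stratification factors".
- **Needs (SCNS-P&C):** "Analyses of supportive-care needs will compare the frequency of individual needs and specific domains", followed by: "Parametric and non-parametric tests, as appropriate, will be used to compare the intervention and control groups". No baseline term, stratification factor, repeated-measures structure or main time-point is named.

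In Appendix A the row "Supportive Care Needs Survey (Carers") is ticked at T0, T3, T6, T12, T18 and T24, the same pattern as HADS.

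On timing, section 4.3.1 ties randomisation to the patient's own questionnaire: "When a participant completes the Baseline Study Questionnaire, the central web-based database will automatically apply the next relevant record in the allocation sequence". Section 4.2.1 has carers nominated after the patient consents, then approached and invited separately. The protocol does not say whether the carer's T0 survey comes before or after allocation.

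**The concern.** Unmet need at follow-up can be expected to depend on unmet need at entry. A comparison that leaves out a scheduled baseline carries between-carer variation that could be removed. Any chance difference between arms at T0 also stays in the estimate.

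This matters somewhat more here than in the main trial. Carers enter by optional nomination and separate consent, so there will probably be fewer carers than patients. The two halves of one carer objective would also be handled differently, although they come from the same people on the same schedule: distress would have an adjusted longitudinal analysis beside its t-tests, and needs would have simple tests alone.

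What is at stake is the width of the interval around an exploratory estimate. The validity of the comparison is not in question.

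**Working it through.** The protocol gives no sample size, power or correlation for the carer outcome, so it has no figure of its own to reproduce.

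**Inputs**
- 1:1 allocation at patient level (section 4.3.1).
- T0 and five follow-up surveys (Appendix A).
- A difference of 0.5 SD regarded as meaningful on the participant scales (section 10.3.2). It is borrowed here as an illustration, because no benchmark is given for SCNS-P&C.
- Assumed: baseline to follow-up correlation *r* = 0.5 (range 0.4 to 0.7); 100 or 60 carers per arm; two-sided α = 0.05; an alternative effect of 0.35 SD.

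**1. Variance of a domain-score contrast.** Adjusting for baseline in a linear model multiplies the variance by 1 − *r*². The equivalent gain in carers is 1/(1 − *r*²) − 1.

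| *r* | 1 − *r*² | Variance removed | Equivalent extra carers |
|---|---|---|---|
| 0.4 | 0.84 | 16% | 19% |
| 0.5 | 0.75 | 25% | 33% |
| 0.7 | 0.51 | 49% | 96% |

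**2. Power.** Power = Φ(*d*·√(*n*/(2(1 − *r*²))) − 1.96). For *n* = 100 and *d* = 0.35 unadjusted, 0.35 × √50 = 2.475, and Φ(0.515) = 70%. With *r* = 0.5, 2.475/0.866 = 2.858, and Φ(0.898) = 82%.

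| Carers per arm | Effect | Unadjusted | Adjusted, *r* = 0.5 |
|---|---|---|---|
| 100 | 0.35 SD | 70% | 82% (77% to 93% for *r* = 0.4 to 0.7) |
| 60 | 0.35 SD | 48% | 60% |
| 100 | 0.5 SD | 94% | 98% |
| 60 | 0.5 SD | 78% | 88% |

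The gain in power therefore depends heavily on the effect size chosen.

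**3. Chance imbalance at T0.** P(difference above 0.2 SD in either direction) = 2(1 − Φ(0.2/√(2/*n*))). For *n* = 100 this is 2(1 − Φ(1.414)) = 16%. For *n* = 60 it is 2(1 − Φ(1.095)) = 27%. An imbalance of 0.2 SD would shift the unadjusted contrast by *r* × 0.2, that is 0.08 to 0.14 SD for *r* = 0.4 to 0.7.

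**4. Validity.** In a simulation of 3,000 trials with no true effect, 100 carers per arm and *r* = 0.5, the rejection rate was 5.3% unadjusted and 4.7% adjusted. Both mean estimates were close to zero. The SD of the estimate was 0.141 unadjusted and 0.121 adjusted. The first matches √(2/100) = 0.141; the second is close to 0.141 × 0.866 = 0.122.

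**5. Scope.** The factor 1 − *r*² applies to domain scores treated as continuous. It does not carry over to the frequency of individual needs.

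**The case against.** The strongest objection is that the sentence on tests is a general placeholder. Section 10.3 defers to a formal statistical analysis plan, which is not at hand. The sentence excludes no adjusted model, and covariates for an exploratory survey are often settled in such a plan. This limits the weight of the point but does not remove it. The protocol is not silent here: it names a class of tests for needs and, in the same paragraph, a different and adjusted method for HADS. A later plan that followed the text would carry the weaker analysis forward.

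The protocol also accepts limited power for this tier: "Although power will be lower for some of these analyses, they are included because of their importance in improving cancer outcomes". That is a fair reason to rate the point as minor, but not a reason to leave a scheduled baseline unused.

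Three stronger readings are tempting, and the document does not support them.

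- A reader might infer that the needs comparison is biased or invalid. It is not: chance imbalance is already allowed for in the test's type I error.
- A reader might infer that carer HADS is analysed only by an adjusted model and needs only by a crude test. HADS also receives plain t-tests at each time-point, including 6 months, so the contrast is between tests plus a model and tests alone.
- A reader might take the carer T0 score to be a clean pre-allocation covariate. The protocol does not say so. Randomisation follows the patient's questionnaire, carers are approached separately, and patients are not blinded (section 4.3.2). If some carers answer T0 after learning the allocation, adjusting for that score could introduce bias that the plain test does not have. This objection stands, and the fix must deal with it.

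**Conclusion.** The point holds as a minor efficiency matter on an exploratory outcome. The stated tests leave out a baseline that Appendix A schedules and that the model inherited by carer HADS uses. For domain scores the avoidable variance is about 16% to 49%, and 25% at a correlation of 0.5.

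This range rests on an assumed correlation. The power figures rest further on assumed carer numbers and an assumed effect size: at 0.5 SD with 100 carers per arm, unadjusted power is already 94%. The gain also requires that the carer T0 survey precedes disclosure of allocation, which the protocol neither states nor rules out.

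**What to change.** In section 10.3.3:

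1. Analyse SCNS-P&C domain scores with the same mixed-effects repeated-measures model as HADS, adjusted for the T0 domain score and the stratification factors, with 6 months as the main time-point.
2. Keep the between-arm comparison of individual need frequencies, adjusted for T0 status by a logistic model where numbers allow.
3. State that the carer T0 survey is to be completed before the patient's allocation is disclosed. Treat T0 surveys completed later as missing baseline in the adjusted model.
4. Report the unadjusted comparison as a sensitivity analysis.

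The cost is slight extra analysis work, with no new visits or questionnaires, since the surveys are already scheduled and the model is already described for HADS. The downside is a dependence on the timing of the carer T0 survey: sites would need to keep to that order and the survey date would have to be available. If many carers complete T0 late, the gain shrinks and the unadjusted comparison carries more weight.

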## 5. **STUDY INTERVENTION**

### 5.1 **Intervention**

The full PROMISE intervention combines the e-PROM tools that participants will complete (5.1.1 and 5.1.2) and the associated implementation strategies (5.1.3). The e-PROM tools use validated instruments (DT and ESAS) that have been used in previous studies, are currently being used in the PROMPTCare system in New South Wales [27-29] and are recommended for use nationally by the Cancer Survivorship Group of the Clinical Oncology Society of Australia (COSA).

In addition to their usual care (Section 5.2), participants randomised to the intervention will be oriented to the use of the e-PROM tool (*My Health My Way* at PAH, TVH; *AboutMe* at RBWH, GCH) at their first treatment visit post-randomisation. A reminder service built into the e-PROM systems will prompt participants to complete the tool 48-72 hours before each subsequent clinic visit (for treatment or follow-up), as previous reports identify this as a feasible time frame for health services to action e-PROM data entered [30]. Participants will also be encouraged to complete the tool monthly between clinic visits to monitor their own progress and facilitate early detection of new problems or exacerbation of existing problems.

When participants arrive for their appointment, the site nurse will check the summary report, to ensure the tool has been completed and, if not, they will help the participant to complete it prior to seeing their clinician. Where feasible, they will give the participant a print-out of the report to take in when they see their clinician; the clinician will also be able to access the report electronically. The report will detail the most recent symptoms entered and their severity (severe, moderate, normal/mild according to standard cut-points) as well as trends over time. Hospital-specific protocols (co-designed with clinical staff – see Section 5.3) will also be used to generate a summary patient-risk profile (e.g. urgent, high, medium, low [30]) and provide recommendations for review/referral. Clinicians will then decide on and prioritise management according to individual patient need.

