### 10.2 **Sample Size Considerations**

Our sample-size has been calculated to achieve a minimum 80% power ( $\alpha=0.05$ ) for our primary outcomes.

- Emergency presentations (measured from linked data that will be close to complete): Previous studies have reported reductions of 17-30% ([9] and personal communication). Assuming a similar baseline rate (1.09/person-year), we require 242 participants per group to detect a 20% reduction with 18 months follow-up.

- HR-QOL: To detect minimally-important differences (where there is no defined minimally-important difference we have used 0.5 standard deviations as recommended [32] we require 70-150 patients per group depending on the outcome. A sample of 200 per group will give >90% power for the primary outcomes in the full population and ~80% power for analyses stratified by e-PROM tool.

Allowing for up to 30% drop-outs (death or withdrawal), we will recruit a minimum of 572 participants (286 per group). We estimate that more than 2000 eligible patients will attend the study hospitals during a 12-month period (data from the Queensland Oncology Analysis System) thus this target is feasible.

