### 10.3 **Statistical Analysis Plan**

Data analysis will be guided by a formal statistical analysis plan that will be finalised prior to any analyses being conducted. All analyses will be intention-to-treat but compliance with the intervention will be assessed and, if there is substantial non-compliance, per-protocol analyses will also be performed. In exploratory sub-group analyses, we will also conduct analyses stratified by e-PROM tool, study site, gender, computer literacy, cancer type and cancer stage (early vs. advanced).

To preserve the blinding during preliminary analyses, the Data Manager will generate datasets with participants' true allocation code replaced by a random dummy code. This will

be replaced by the true code when we perform the final analyses (as in the D-Health trial [26]).

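### Repeating the arm comparisons within subgroups does not test effect modification, and a difference between e-PROM tools cannot be separated from a difference between hospitals

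*Protocol*

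**What the plan says.** Section 10.3.3 gives the method: "We will repeat the primary and secondary analyses above for sub-groups of participants defined by (i) study site", followed by e-PROM tool, cancer type (high or low mortality), curative or palliative treatment, sex and computer literacy. It then gives the aim: "This is to examine effect modification and identify scenarios where e-PROM tools are potentially most effective and those where their effectiveness could be improved". Its one caveat concerns power: "We recognise that statistical power will be more limited for some of these stratified comparisons".

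Section 10.3 describes the same approach: "In exploratory sub-group analyses, we will also conduct analyses stratified by e-PROM tool, study site, gender, computer literacy, cancer type and cancer stage". This list includes cancer stage and omits treatment intent; the list in 10.3.3 does the reverse.

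The analyses to be repeated (10.3.1 and 10.3.2) are comparisons of intervention with control: t-tests, chi-squared tests, linear and mixed models, and Poisson regression. The protocol names no interaction term or heterogeneity test.

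Section 5.1 ties each hospital to one tool: "My Health My Way* at PAH, TVH; *AboutMe* at RBWH, GCH". Section 4.3.1 randomises patients 1:1, with hospital as one of the stratification factors. Section 10.3.1 lists both site and e-PROM tool as covariates in the FACT-G model. Section 10.2 states that 200 per group gives about "80% power for analyses stratified by e-PROM tool".

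**The concern.** Effect modification means that the intervention effect differs between subgroups. A test within each subgroup asks a different question, namely whether there is an effect in that subgroup. Two subgroups with the same true effect can easily fall on opposite sides of the 5% threshold by chance, and two with different effects can both be significant. The stated method therefore does not answer the stated question.

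The tool subgroup has a second difficulty. Tool is a property of the hospital and was not randomised. Section 5.1 also provides for hospital-specific protocols for risk profiling and referral, so the response to a report may vary by hospital along with the platform. A difference in effect between tools may be a difference between hospitals.

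At stake is what is said about where the tools work best, which is the declared purpose of these analyses. The overall comparison of e-PROM use with usual care is not affected.

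**Working it through.** **Inputs**
- 200 analysed per group, 30% drop-out, 286 recruited per group, alpha 0.05, about 80% power by tool (10.2). Sidedness is not stated; two-sided is assumed.
- Clinically meaningful difference 0.5 SD (10.3.1).
- Event rate 1.09 per person-year, 20% reduction, 18 months, 242 per group (10.2).
- Even split by tool, assumed: 100 per arm per tool. The site targets in 3.3 support this. Read per hospital they total 2×150 + 2×110 = 520 to 2×175 + 2×145 = 640, which brackets 572, and each tool has one larger and one smaller hospital.

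**The protocol's own figures**
- Recruitment: 200 / (1 − 0.30) = 286 per group, as stated.
- Within-tool power = Φ(d / √(2/100) − 1.96):
  - d = 0.5: Φ(3.54 − 1.96) = 94%
  - d = 0.4: Φ(2.83 − 1.96) = 81%
  - d = 0.3: Φ(2.12 − 1.96) = 56%
- The stated 70 to 150 per group imply, at 80% power, effects of 0.47 to 0.32 SD. Within-tool power over that range is 92% to 63%. The figure of about 80% is therefore plausible, although the effect size behind it is not given.

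**Chance of a false contrast when both tools have the same true effect**

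With within-tool power p, the chance that exactly one tool is significant is 2p(1 − p).

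| Basis | p | Exactly one significant |
|---|---|---|
| Protocol's own figure | 0.80 | 32% |
| 0.5 SD | 0.942 | 11% |
| 0.3 SD (illustrative, not in the protocol) | 0.564 | 49% |

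For the event rate with 242 / 2 = 121 per arm per tool:
- SE of the log rate ratio = √[(1/(1.09×1.5) + 1/(0.872×1.5)) / 121] = 0.107
- Within-tool power = Φ(0.223 / 0.107 − 1.96) = 55%
- Exactly one significant: 2 × 0.553 × 0.447 = 49%

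**What an interaction test could detect**
- SE of the difference between the two tools' effects = √(4/100) = 0.20 SD, against √(2/200) = 0.10 SD for the overall effect.
- Difference of 0.5 SD: Φ(2.5 − 1.96) = 71% power.
- Difference of 0.4 SD: Φ(2.0 − 1.96) = 52% power.
- Detectable with 80% power: (1.96 + 0.84) × 0.20 = 0.56 SD.
- Event rate, ratio of rate ratios 0.8: SE = 0.107 × √2 = 0.151; Φ(0.223 / 0.151 − 1.96) = 32% power.

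**Aliasing of tool and site**

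As a baseline covariate, tool takes the same value for every patient at a hospital. Four site indicators plus a tool indicator form five columns of rank 4, because tool is the sum of two of the site indicators. With site in the model as a fixed factor, tool adds no information and its coefficient cannot be estimated.

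**The case against.** Four points weigh on the other side.

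- **A separate analysis plan is promised.** Section 10.3 says a formal plan will be finalised before any analysis, and it may specify interaction tests. Subgroup estimates are also a normal first step. This limits the weight of the point but does not remove it: 10.3.3 pairs a method with an aim that the method does not meet, which is more than detail left for later.
- **The faulty inference is not written down.** A reader might infer that effect modification will be declared when one subgroup is significant and another is not, or that a claim about the better tool is planned. Neither is in the protocol. The hypotheses treat the tools as one intervention, the subgroup analyses are labelled exploratory, and the stated aim is hedged. This stands.
- **Comparisons within a tool are sound.** A reader might infer that confounding of tool with hospital biases the tool-specific results. It does not, because patients are randomised within hospital. Only attribution of a between-tool difference to the tool is unsupported. The allocation of tools is also openly stated in 5.1, and no analysis can undo it.
- **The power statement in 10.2 is not wrong.** It could be misread as power to compare the tools, but it speaks of stratified analyses, so it is within-tool power. It needs no correction.

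**Conclusion.** The point holds as a mismatch between method and aim in exploratory analyses. Sections 10.3 and 10.3.3 set only within-subgroup repeats, which cannot show that the effect differs between subgroups. With identical effects in both tools, separate tests would give a misleading split in about 32% of trials at the protocol's own power. The figure ranges from about 11% at 0.5 SD to about 49% at 0.3 SD; the latter effect is illustrative and should not be the headline. These figures assume two-sided 5% tests, an even split by tool, equal SDs and a normal approximation.

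Separately, and on no numerical assumption, tool is determined by hospital. A between-tool difference therefore cannot be attributed to the tool, and tool is redundant in the FACT-G model once site is included. The two subgroup lists disagree on cancer stage and treatment intent, which is a minor drafting inconsistency.

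The documents do not support reading this as a threat to the primary or secondary conclusions, or to the within-tool comparisons.

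**What to change.** - In 10.3.3, assess each modifier by an arm-by-subgroup interaction in the relevant outcome model. Report the interaction estimate and the subgroup estimates with 95% confidence intervals, and state that no conclusion on effect modification will be drawn from separate within-subgroup p-values.
- Describe any tool contrast as a contrast between hospital pairs (PAH and TVH against RBWH and GCH).
- In 10.3.1, drop e-PROM tool as a covariate where site is in the model.
- Use one subgroup list in 10.3 and 10.3.3, settling whether cancer stage, treatment intent or both are included.

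The cost is wording only; recruitment, data collection and conduct are unchanged. The drawback is low interaction power, so a non-significant interaction would not show that effects are equal, and the results remain exploratory. An interaction test does not separate tool from hospital, so the wording on hospital pairs is needed as well.
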